#### **11.11.5.2. Pharmacokinetics**

Refer to section 7.5 in the protocol

All pregnant participants who elect to remain in the study will have the following PK samples obtained at each LA injection visit throughout the pregnancy and at the first postpartum LA injection visit:

- Blood samples for evaluation of total CAB (2mL each) and total RPV (2mL each) plasma concentrations.
- Blood sample for evaluation of unbound CAB (9mL each) plasma PK concentration.

. All PK samples will be trough levels and will be collected prior to the scheduled LA injection. The pre-dose trough PK sample is to be collected within 15 minutes prior to the LA dose, on the day of the study visit.

For participants pregnant during the Long Term Follow Up phase, plasma concentrations of cabotegravir and rilpivirine will be collected as per Section 7.1 Time and Events table.

Please refer to the SPM for PK sample collection, processing, and shipping instructions. The actual date and time of each PK sample collection will be recorded in the eCRF.

## 11.12. Appendix 12: Device Deficiencies: Definition and Procedures for Recording, Evaluating, Follow-up, and Reporting in Medical Device Studies

The definitions and procedures detailed in this appendix are in accordance with ISO 14155 and the European Medical Device Regulation (MDR) 2017/745 for clinical device research, and the US Food and Drug Administration (FDA) combination product reporting rule, 21 CFR 4, Subpart B.

Both the investigator and the sponsor will comply with all local medical device reporting requirements for medical devices.

The detection and documentation procedures described in this protocol apply to all medical devices used in the study (see Section 6.14 for the list of medical devices).

### 11.12.1. Definition of Device Deficiency

#### Device Deficiency Definition

- A device deficiency is an inadequacy of a medical device with respect to its identity, quality, durability, reliability, safety, or performance. Device deficiencies include malfunctions, use errors, and inadequacy of the information supplied by the manufacturer.

### 11.12.2. Recording and Follow-Up of AE and/or SAE and Device Deficiencies

#### AE, SAE and Device Deficiency Recording

- When a device deficiency occurs, with or without an associated AE/SAE, it is the responsibility of the investigator to review all applicable documentation (e.g., hospital progress notes, laboratory reports, and diagnostics reports) related to the event.
- The investigator will then record all relevant device deficiency information on the appropriate form. If applicable, any associated AE or SAE will be documented in the participant's medical records, in accordance with the investigator's standard clinical practice. There may be instances when copies of medical records for certain cases are requested by the sponsor. In this case, all participant identifiers, with the exception of the participant number, will be redacted on the copies of the medical records before submission to the sponsor.
- The investigator will attempt to fully describe the device deficiency and provide details on any treatment provided.
- For device deficiencies, it is very important that the investigator describe any corrective or remedial actions taken to prevent the deficiency's recurrence.
  - A remedial action is any action other than routine maintenance or servicing of a medical device where such action is necessary to prevent the recurrence of a device deficiency. This includes any amendment to the device design to

prevent recurrence.
Assessment of Intensity of associated AE/SAEs

 
If an AE or SAE is associated with a device deficiency, the investigator will make an assessment of intensity for each AE or SAE as outlined in Section 7.4.3
 

Follow-up of device deficiency

 
The investigator is obligated to perform or arrange for the conduct of supplemental measurements and/or evaluations as medically indicated or as requested by the sponsor to elucidate the nature of the device deficiency and any associated AE or SAE as fully as possible
 
New or updated information regarding the device deficiency will be recorded in the originally completed medical device deficiency report form.
 
If there is an associated SAE with the device deficiency, the investigator will submit any updated SAE data to GSK within 24 hours of receipt of the information.
 

### 11.12.3. Reporting of Medical Device Deficiencies for participants

Reporting to GSK

 
NOTE: There are additional reporting obligations for medical device deficiencies that are potentially related to SAEs that must fulfill the legal responsibility to notify appropriate regulatory authorities and other entities about certain safety information relating to medical devices being used in clinical studies.
 
Medical device deficiencies that are not related to an AE or SAE should be reported via email to [contact], using the medical device deficiency report form.
 
If the medical device deficiency is related to a non-serious AE and not linked to an SAE, please send the medical device deficiency report form via email to [contact] only. The eCRF for the subject should also be updated with AE information, as outlined in Section 7.4.3
 
If the device incident is linked to an SAE, please email the medical device deficiency report form, within 24 hours, to both [contact] (or [contact]) and [contact]. The SAE form should also be reported, as outlined in Section 7.4.3. The eCRF for the subject should also be updated with the SAE information.
 
GSK will review all device deficiencies and determine and document in writing whether they could have led to an SAE. These device deficiencies will be reported to the regulatory authorities and IRBs/IECs as required by national regulations.
 
Contacts for Medical Device Deficiency reporting can be found in the medical device deficiency report form.
 

#### 11.12.4. Reporting of Medical Device Deficiencies for Associated Person

##### Reporting to GSK

If an Associated Person (i.e. spouse, caregiver, site staff...) experiences a device deficiency, the medical device deficiency information and any associated AE/SAE information will be reported to GSK. The associated person will be provided with the safety reporting information and authorization to contact physician letter.

If follow up is required, authorization to contact physician (or other licensed medical practitioner) must be signed to obtain consent.

- Medical device deficiencies that are not related to an AE or SAE should be reported via email to [[contact]](mailto:[contact]), using the medical device deficiency report form.
- If the medical device deficiency is related to a non-serious AE and not linked to an SAE, please send the medical device deficiency report form with details of the associated AE via email to [[contact]](mailto:[contact]) only.
- If the device incident is linked to an SAE, please email the medical device deficiency report form, within 24 hours, to **both** [[contact]](mailto:[contact]) (or [contact]) **and** [[contact]](mailto:[contact]). The associated SAE form should also be reported to [[contact]](mailto:[contact]) (or [contact]).
- GSK will review all device deficiencies and determine and document in writing whether they could have led to an SAE. These device deficiencies will be reported to the regulatory authorities and IRBs/IECs as required by national regulations.
- Contacts for Medical Device Deficiency reporting can be found in the medical device deficiency report form.

#### **11.13.1. Sub-study Amendment Background**

Cabotegravir/rilpivirine (CAB/RPV) long acting (LA) has been approved for the treatment of HIV-1 infection as a complete regimen in adults to replace the current antiretroviral regimen in many geographical regions of the world including the United States, Canada, Europe and Australia with additional countries approaching regulatory approval. CAB/RPV LA is administered via gluteal injections for monthly or every two months dosing for clinic-based administration by a Health Care Provider (HCP). As more patients are experiencing this new treatment paradigm, it is becoming apparent that HIV stigma and issues surrounding HIV disclosure, while improved, have not totally been eradicated. As more HIV infected individuals opt for LA therapy to control their HIV infection, many patient groups and other activist communities are requesting continued research and development in alternative injection sites. These measures may improve overall treatment compliance for patients with difficulty adhering to monthly or every other month office visits and may improve any residual stigma that patients may still be experiencing during their engagement with various healthcare systems.

An ongoing Phase 1, healthy volunteer open-label study (208832) is evaluating the pharmacokinetics (PK) and tolerability of cabotegravir and rilpivirine long-acting injections following intramuscular administration in the vastus lateralis muscle (further referred to as thigh) in 15 study participants (n= 9 male, n=6 female; BMI (kg/m^2) median 30.3). All subjects received a 4-week oral lead in (OLI) with daily cabotegravir 30 mg and rilpivirine 25 mg, and after a two week wash out, 14 participants received single 600 mg CAB LA and 900 mg RPV LA injections. One participant was withdrawn after the OLI phase and before injection due to confirmed pregnancy.

[figure not shown]
PK sampling for measurement of plasma CAB and RPV in this on-going Phase 1 study was performed at the following timepoints: D1, 2, 4, 5, 7, 8, 10, 15, 17, 22, 28 (week 4) post injection with longer term PK evaluations also obtained at weeks 8, 12, 24, 36, and 52 post the single CAB/RPV injections. Safety and tolerability data through week 12

Covariates were resampled 1000 times from the participants in the thigh PK study (n=14), generating 1000 virtual subjects. Individual PK parameters of the virtual subjects were calculated using subject-specific covariates and using the population parameter estimates including residual variability, subject-specific NONMEM inter-individual errors (ETAs) sampled from the distributions that are decided by the estimated variance-covariate matrix of between-subject variability from the final PopPK model. Concentration-versus-time profiles of the virtual subjects were calculated using the individual PK parameters of the virtual subjects following a single CAB LA injection of 600 mg. Median and 5th and 95th percentiles of the simulated concentration-versus-time profiles of the virtual subjects were calculated and plotted.

**Figure 20 Preliminary RPV Concentrations following a Single 900 mg IM injection to the lateral thigh (n=14) Phase 1 Study 208832**

Note: the predictions are based on population PK model for IM gluteal injections  
 Open black circles: observed data thigh injection Phase 1 study; Blue dotted line (upper, lower vertical blue line), red closed circles: geometric mean (5th, 95th percentile), median of observed data thigh injection Phase 1 study  
 12 ng/mL: protein binding adjusted IC90  
 17.3 ng/mL: observed 5th percentile Ctau 4 weeks after first IM gluteal injection in ATLAS/FLAIR

**11.13.2. Sub-study Amendment rationale**

Data through week 12 from the Phase 1 study, as described above, suggest well tolerated thigh injections with CAB and RPV PK concentrations similar between thigh and gluteal injections. This study provides the evidence to evaluate thigh injections in HIV-infected individuals already receiving either Q4W or Q8W dosing of CAB/RPV LA. Instead of designing a separate study, A2M will be amended to allow an assessment of thigh injections as an alternative injection site than what is currently allowed in the prescribing

information to evaluate the PK parameters, safety, tolerability and virologic response in HIV-1 infected participants receiving CAB and RPV LA.

This sub-study will assess the comparability of CAB and RPV PK (and other parameters) following gluteal and thigh injections. Absorption of CAB following injection into an IM site is described as a first order process with an absorption rate constant,  $K_A$  LA. This absorption rate constant is the model parameter that is most sensitive to alterations in physiology and drug administration; the factors of gender, BMI and needle length all influence CAB absorption kinetics and are covariates for the parameter  $K_A$  LA. Plasma trough concentration ( $C_{tau}$ ) is the exposure parameter most associated with cabotegravir efficacy with an identified 5th percentile of population exposure used to determine efficacious regimens and interventions. Importantly, CAB has a wide therapeutic index where despite approximately 6-fold difference in CAB  $k_a$  values across the population (including a 2-fold mean difference between males and females) there is no difference in Phase 3 efficacy.

The main PK parameters of interest include  $C_{tau}$ , concentrations post dose [ $\sim C_{max}$ ], and AUC (0- $C_{tau}$ ). CAB and RPV PK parameter will be evaluated by comparing thigh injection with gluteal injection using the ratio of the geometric mean of thigh injection to the geometric mean of the gluteal injection for a PK parameter within each treatment arm (Q8W, Q4W) and each analyte (CAB, RPV). No formal statistical hypotheses are to be tested, and the sample size was selected mainly based on the precision of the geometric mean ratio estimate (thigh injection vs gluteal injection) and the data sufficiency to assess the safety parameters within 16 weeks of thigh injection phase.

Moreover, additional safety and tolerability data following thigh injections for both regimens will also be collected to better characterise the safety/tolerability profile of IM injections to the lateral thigh.

[figure not shown]
The study's main objective is to assess the comparability of PK between thigh vs gluteal injections in HIV-1 infected participants to support at home IM strategy for LA self-administration by demonstrating similar safety/tolerability and PK parameters between gluteal and thigh administration.

### 11.13.3. Sub-study Amendment: Objectives and Endpoints

Objectives	Endpoints
Primary Endpoint	
Pharmacokinetic	
To evaluate the PK of monthly and every two months dosing of CAB LA and RPV LA injections following intramuscular administration in the vastus lateralis (thigh) muscle (compared to gluteal injections) in HIV-1 infected participants currently	Plasma PK parameters for CAB LA and RPV LA ( $C_{tau}$ , concentrations post dose [ $\sim C_{max}$ ], and area under the curve [AUC (0- $\tau$ )]) for thigh injections during the thigh injection phase compared with similar PK parameters

Objectives	Endpoints
enrolled in the A2M sub-study	for gluteal injections.
Secondary Endpoints	
Safety and tolerability	
To assess safety and tolerability of monthly and every two months dosing of CAB LA and RPV LA following intramuscular injections in the vastus lateral (thigh) muscle in HIV-1 infected participants currently enrolled in the A2M sub-study.	
Incidence and severity of ISRs and AEs of special interest during the thigh injection phase.
 
Proportion of participants who discontinue treatment due to ISRs and AEs of special interest during the thigh injection phase.

Virologic Efficacy	
To assess the ability to maintain virologic suppression (HIV-RNA < 50 copies) in subjects who transition to thigh administrations of CAB and RPV after receiving at least 3 years of gluteal injections.	
 
• Proportion of participants with plasma HIV-1 RNA <50 c/mL over time (including at Week 16) during the thigh injection phase using the FDA Snapshot algorithm.
 
• Proportion of participants with plasma HIV-RNA ≥50 c/mL over time (including at Week 16) as per Food and Drug Administration (FDA) Snapshot algorithm during the thigh injection phase.
 
• Proportion of participants with protocol-defined confirmed virologic failure (CVF) during the thigh injection phase.
 

To assess viral resistance in participants experiencing protocol-defined confirmed virologic failure.	Incidence of treatment emergent genotypic and phenotypic resistance to CAB, RPV during the thigh injection phase.
Health Outcomes	
To assess patient reported outcomes during the thigh injection phase by administering the following health outcome measurements: Numerical Rating Scale (NRS) and HIVTSQ.	
 
• Numerical Rating Scale (NRS): To assess the tolerability of injections during both the Thigh and Gluteal Injection Phase
 
• HIVTSQ (both s and c versions):
 

[figure not shown]
Objectives	Endpoints
	
To measure levels of satisfaction and detect change in satisfaction when switching from gluteal to thigh injections in total “treatment satisfaction” score, and individual item scores of the HIV Treatment Satisfaction Questionnaire (HIVTSQ) during the Thigh Injection Phase as well as the change from thigh during the Return to Gluteal Phase.

To assess participant’s preference of thigh injections during the thigh injection phase compared to gluteal injections.
	
Preference Questionnaire: To assess patient’s preference, and reasons for preference, for injections received during the Thigh Injection Phase compared with prior gluteal injections as well as for injections received during the Return to Gluteal phase compared with prior thigh injections.

Exploratory Endpoints
	

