#### 11.13.4.6. Sub-study Amendment Withdrawal/Stopping Criteria

Participants meeting **Withdrawal/Stopping criteria as per Section 5.5** will discontinue the study treatment and be withdrawn from both A2M and the sub-study, and will complete assessments per T&E table in Section 7.1 and enter in the Long Term Follow-Up phase.

Participants who decide to discontinue their participation in the sub-study **for non-safety reasons** (refer to Section 5.5), including participants who require **Oral Bridging** during the sub-study **or** participants who decide to discontinue their participation in the sub-study due to **injection-site (thigh) related tolerability reasons**:

- In countries where the marketed products of CAB and RPV LA are **not yet locally available**, such patients will be allowed to transition back to the main study and continue with IM gluteal injections per the randomized dosing schedule.
- In countries where the marketed products of CAB and RPV LA are **locally available**: patients will be invited to return to gluteal injections in the main study and receive 1 more gluteal injections (additional injections might be required if requested by MM) before transitioning to marketed product as described in Section 4.2.4 and Section 5.6

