#### **11.13.8.4.2. Secondary and Exploratory Analyses**

The proportion of participants with HIV-1 RNA  $\geq 50$  c/mL and HIV-1 RNA  $< 50$  c/mL during the thigh injection phase will be summarized using FDA Snapshot algorithm for the ITT-E population for the substudy. Proportion of participants with protocol-defined confirmed virologic failures will also be summarized over time.

The proportion of participants reporting AEs will be tabulated for each treatment group. The following summaries of AEs will be provided:

- Incidence and severity of all AEs
- Incidence and severity of treatment related AEs
- Incidence and severity of AEs leading to withdrawal
- Incidence of SAEs
- ISR AEs from study drug injections at the event level and subject level, separately.
- Change from baseline (latest non-missing value prior to the first thigh injection) in laboratory will be summarized by visit and treatment group.
- The incidence of observed genotypic and phenotypic resistance to NRTIs and INIs, PIs, and NNRTIs will be summarized by treatment arm for subjects meeting confirmed virologic failure criteria.

The health outcomes analyses include analyses of data collected from the following four questionnaires, HIVTSQ (both s and c versions), NRS and Preference between thigh and gluteal injections. Further details will be provided in the RAP.

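### Thigh sub-study: read with the protocol's own exit rule, the endpoint for discontinuation due to ISRs and AEs of special interest omits participants who give up the thigh site for intolerance and return to gluteal injections

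*Protocol*

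**What the plan says.** The sub-study's safety objective in Protocol 11.13.3, which concerns the thigh site, is "To assess safety and tolerability of monthly and every two months dosing of CAB LA and RPV LA following intramuscular injections in the vastus lateral". One of its two endpoints is the incidence and severity of injection-site reactions (ISRs) and AEs of special interest (AESIs). The other is the "Proportion of participants who discontinue treatment due to ISRs and AEs of special interest during the thigh injection phase". Section 11.13.2 says the sub-study is meant to support at-home self-administration "by demonstrating similar safety/tolerability and PK parameters between gluteal and thigh administration".

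Section 11.13.4.6 describes two ways out:

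- Participants who meet the stopping criteria of Section 5.5 "will discontinue the study treatment and be withdrawn from both A2M and the sub-study".
- Participants who leave the sub-study "for non-safety reasons" form the second group. The same sentence takes in those who need oral bridging and those who leave for "injection-site (thigh) related tolerability reasons". Where the products are not yet marketed locally, "such patients will be allowed to transition back to the main study and continue with IM gluteal injections per the randomized dosing schedule". Where they are marketed, participants are invited to take at least one more gluteal injection in the main study before moving to marketed product.

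Section 11.13.8.4.2 lists, among the AE summaries, "Incidence and severity of AEs leading to withdrawal". It does not say whether the withdrawal is from thigh dosing, the sub-study or the main study.

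**The concern.** Someone who finds thigh injections intolerable but has no problem with the drugs takes the second way out and goes on receiving the same two drugs in the gluteal muscle. Section 11.13.4.6 does not describe that person as discontinuing study treatment; it uses that description only for the first group. If the endpoint in 11.13.3 is programmed with the same meaning, the proportion discontinuing because of ISRs or AESIs leaves out participants who stopped the thigh site because of the thigh site.

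This matters because the sub-study asks about a site of injection, not about a new drug. Under 11.13.4.1.1 every participant has had at least 152 weeks on the regimen. It is therefore reasonable to expect site-specific intolerance to lead back to gluteal dosing more often than to stopping both drugs. The omission works in one direction: it makes the thigh look better tolerated than it was.

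**Working it through.** **Step 1: set the sections side by side.**

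| Participant | Exit under 11.13.4.6 | CAB LA + RPV LA afterwards | Counted if the endpoint means all study treatment | Counted if it means thigh injections |
|---|---|---|---|---|
| Meets Section 5.5 criteria because of an ISR or AESI | Leaves both studies | Stopped | Yes | Yes |
| Stops for thigh-site intolerance | Leaves the sub-study | Continues, gluteal | No | Yes |
| Needs oral bridging | Leaves the sub-study | Resumes, gluteal | No | No |

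The readings differ only in the second row, which is the group a thigh-tolerability endpoint most needs to count. Nothing in the protocol text at hand says that 11.13.3 intends the last column.

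**Step 2: reproduce the plan's precision figures (11.13.8.2).** The input is n = 41 per arm.

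- One-sided 95% Clopper-Pearson upper limit with no events: 1 − 0.05^(1/41) = 7.05%. The protocol states 7.0%.
- Chance of at least one event at a true rate of 0.5%: 1 − 0.995^41 = 18.6%. The protocol states about 18%.

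Both agree, so no stated figure is in dispute.

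**Step 3: what each uncounted participant is worth.** One of 41 is 1/41 = 2.4 percentage points. Suppose k participants in an arm stop thigh injections for intolerance and return to gluteal dosing, and nobody discontinues under Section 5.5. On the all-study-treatment reading the endpoint is 0/41 with an upper limit of 7.0%. If they are counted, the upper limit U solves P(X ≤ k | n = 41, U) = 0.05:

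| k (assumed) | k/41 | One-sided 95% upper limit |
|---|---|---|
| 0 | 0.0% | 7.0% |
| 1 | 2.4% | 11.1% |
| 2 | 4.9% | 14.6% |
| 3 | 7.3% | 17.8% |
| 5 | 12.2% | 23.9% |

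**Step 4: how likely such participants are.** The protocol gives no rate, so these true rates p are assumptions. The expected number is 41p and the chance of at least one is 1 − (1 − p)^41.

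| p (assumed) | Expected per arm | Chance of at least one per arm |
|---|---|---|
| 2% | 0.8 | 56% |
| 5% | 2.1 | 88% |
| 10% | 4.1 | 99% |

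**The case against.** The strongest reply is that 11.13.3 never defines what is discontinued. The endpoint sits in the sub-study's own table, under an objective about thigh injections, and is limited to the thigh phase. The treatment given in that phase is the thigh injection, so stopping it for an ISR fits the words. That reading is open, and a reader who infers that the endpoint certainly excludes these participants goes further than the text. What stands is that the only comparable wording in 11.13.4.6 points the other way and that the two readings give different counts.

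Three further points stand in part:

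- **The non-safety label.** The sentence in 11.13.4.6 can be parsed with thigh intolerance as a category of its own beside the non-safety reasons. It also governs where participants go next, not how AEs are recorded. Either way they stay on CAB LA + RPV LA, so the gap remains.
- **The AE table.** One might infer that the summary of AEs leading to withdrawal also drops these participants. The protocol does not support that. The table does not say what the withdrawal is from, and 11.13.4.6.3 speaks of withdrawing from the sub-study for a pregnant participant who may continue gluteal injections. An ISR that led to leaving the sub-study could be tabulated there as written.
- **Other measures.** ISR incidence and severity, ISR summaries by event and by subject, pain on the NRS, satisfaction and preference are all collected. They describe the experience of thigh injections but do not give the proportion who gave up the site because of it.

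No hypothesis is tested (11.13.8.1), the primary PK comparison is unaffected, and the only thigh data shown are reassuring: after single injections in the Phase 1 study, 13 of 14 ISRs were mild and one was moderate (11.13.1). This limits the consequence but does not settle what the endpoint counts.

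**Conclusion.** The point holds in a limited form. Read with the usage of 11.13.4.6, the secondary endpoint in 11.13.3 omits participants who abandon the thigh site because of intolerance and so understates thigh intolerance. As written it can also be read to include them, so the reported proportion would depend on an undefined term.

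A reader might go on to infer that the endpoint must come out near 0% however poorly the thigh is tolerated. The protocol does not support that: participants who meet Section 5.5 criteria because of an ISR or AESI are counted on either reading, and AESIs need not concern the injection site.

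The size cannot be stated. It is 2.4 percentage points per uncounted participant. Two such participants in an arm, an assumed number close to the 2.1 expected at a 5% rate, would turn 4.9% (upper limit 14.6%) into a reported 0% (upper limit 7.0%). These figures assume 41 treated per arm and no discontinuation under Section 5.5. That section lies in the part of the protocol not at hand, so the exact boundary between the two exits could not be checked. The change is worth making because it alters what a named secondary endpoint counts and costs almost nothing.

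**What to change.** Reconcile 11.13.3, 11.13.4.6 and 11.13.8.4.2:

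1. Define the endpoint as the proportion who stop thigh injections during the Thigh Injection Phase because of an ISR, an AESI or thigh-site tolerability, whether or not gluteal CAB LA + RPV LA continues.
2. Report discontinuation of all study treatment as a separate line, since it is a different and legitimate safety quantity.
3. State that the summary of AEs leading to withdrawal includes withdrawal from the sub-study.
4. Record exits for thigh-site tolerability separately from oral bridging and other non-safety reasons.

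The cost is the wording of one endpoint and one table, plus a mapping of the recorded reason for leaving the sub-study. No visit, sample or extra participant is needed, and no change to clinical management is implied.
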